9.2.1. Inclusion criteria

Patients who met all of the following sample selection criteria will be included:

- Male with ≥ 1 diagnosis of PC (International Classification of Diseases, 10th Revision, Clinical Modification [ICD-10-CM] C61)
- Had ≥ 2 prescriptions of relugolix on or after the first observed PC diagnosis. The initiation date of relugolix will be selected as the **index date**
- At least ≥ 18 years old as of the index date
- Had continuous activity in the data for ≥ 365 days prior to the index date and ≥ 90 days since the index date (unless died within 90 days). The **baseline period** will be defined as the 365-day period prior to the index date. The **follow-up period** will be from the index date to the end of continuous eligibility, data availability, or death, whichever happened first

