9.2.2. Exclusion criteria

Patients will not be included from the study if they:

[figure not shown]
- Had surgical castration (bilateral orchectomy) any time before the index date

PFIZER CONFIDENTIAL

CT24-WI-GL02-RF02 5.0 Non-Interventional Study Protocol Template For Secondary Data Collection Study 01-
Aug-2023
Page 17 of 41

- Had evidence of clinical trial participation within 30 days prior to the index date or within 90 days since the index date
- Had any other primary cancer (excluding non-melanoma skin cancer) during the baseline period

Figure 1. Sample selection for PC patients initiated relugolix

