Comorbidities	A binary variable (yes/no) will be created for patients with a diagnosis of each of the following comorbidities during the baseline period: 
• Hypertension• Hyperlipidemia• Diabetes• Urinary tract infection• Chronic obstructive pulmonary disease• Arrhythmia• Congestive heart failure• Myocardial infarction• Stroke• Angina pectoris• Inflammatory bowel disease• Acute coronary syndrome• Sexual dysfunction• Depression• Anxiety• Hot flashes• Cognitive impairment• Major adverse cardiovascula event (defined by any evidence of cardiomyopathy, heart failure, ischemic heart disease, myocardial infarction, pulmonary embolism, or stroke)
PSA	Baseline PSA value (among available) based on the PSA value closest to the index date during the 90-day window (or 180-day, to be finalized based on the number of patients with non-missing PSA value in these time frames) on or prior to the index date will be evaluated.
Testosterone	Baseline testosterone value (among available) based on testosterone value closest to the index date during the 90-day window (or 180-day; will be consistent with the time window for baseline PSA) on or prior to the index date will be evaluated.
Metastatic vs. non-metastatic PC	A binary variable for patients with metastatic vs. non-metastatic PC will be created. Metastatic PC will be

Variable	Operational definition
	defined as having evidence of metastasis during the baseline period or within 90 days since the index date.
ADT naïve vs. ADT experienced	A binary variable for patients who were ADT naïve vs. ADT experienced will be created. ADT naïve will be defined as having no records of any systemic ADT treatment ever based on all available data prior to the index date (i.e., including baseline period data and any available data prior to the baseline period). Systemic ADT treatment includes LHRH agonists and GnRH antagonists (i.e., degarelix, relugolix, goserelin, histrelin, leuprolide, triptorelin)

Table 3. Treatment patterns, adherence, persistence, and clinical variables during the follow-up period

Variable	Operational definition

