9.5. Study size

As no priori hypotheses are specified, sample size calculations are not applicable. The number of patients eligible for the study will be determined in accordance with the sample selection conducted per the criteria described in Section 9.2.

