The same descriptive analysis described in [Section 9.7.1](#) will be conducted in Black and non-Hispanic White patients separately. If the sample sizes allow, SMD will be calculated to compare the patient baseline characteristics between Black vs. non-Hispanic White cohorts. Additionally, p-values from appropriate statistical tests (e.g., t-tests or rank-sum tests for continuous variables and chi-square tests for categorical variables) comparing Black vs. non-Hispanic White cohorts will be reported.

9.7.6. Data analysis for Objective 6: To describe and compare time to treatment changes between Black and non-Hispanic White patients with PC who initiated relugolix

The same descriptive analyses described in Section 9.7.2.3 will be conducted in Black and non-Hispanic White patients separately. Unadjusted and adjusted comparisons between the two race groups will be conducted. Cox proportional hazards (PH) regressions will be used to compare the time to treatment changes between the two race groups. Patient characteristics to be included in the adjusted models will be selected based on findings in Section 9.7.5 and clinical input.

9.7.7. Data analysis for Objective 7: To estimate and compare adherence and persistence with relugolix between Black and non-Hispanic White patients with PC who initiated relugolix

The same descriptive analyses described in Section 9.7.3 will be conducted in Black and non-Hispanic White patients separately. Unadjusted and adjusted comparisons between the two race groups will be conducted. Generalized linear models will be used to compare adherence to relugolix between the two race groups. Cox PH regressions will be used to compare persistence between the two race groups. Patient characteristics to be included in the adjusted models will be selected based on findings in Section 9.7.5 and clinical input.

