9.8. Quality control

Best practice guidelines will be followed to ensure project quality, including structured organization of project materials (e.g., data extracts, statistical software programs, output tables) and standard internal audit process. The audit process both confirms the validity of the analytical approach and ensures that all programs and results are accurate.

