ANNEX 1. LIST OF STAND-ALONE DOCUMENTS

None.

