Cognitive impairment	G30, G31.0, F01, F05, R41.0, R41.82, F10.1, F10.2, G31.2, G31.83, F02, F03, G31.1, G31.84, F06.7, R41.3, R41.81, R41.840
Hot flashes	R23.2
Primary cancers	C00-C21, C22.1-C22.7, C23-C76, C80.1, C80.2, C81-C96, C7A

Abbreviations: ICD-9-CM: International Classification of Diseases, 9th Revision, Clinical Modification; ICD-10-CM: International Classification of Diseases, 10th Revision, Clinical Modification; NCI: National Cancer Institute

[1] Source: Quan, Hude, et al. Coding algorithms for defining comorbidities in ICD-9-CM and ICD-10 administrative data. Medical care (2005): 1130-1139. Adapted using codes found in NCI Comorbidity Index Overview: <https://healthcaredelivery.cancer.gov/seermedicare/considerations/comorbidity.html>

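### The only visible code list for the other-primary-cancer exclusion does not match the criterion: it includes C61 and C44 and leaves out C22.0 and C22.8 (minor)

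*Combined protocol and SAP*

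**What the plan says.** Section 9.2.1 identifies the study disease by a code printed in the criterion itself: "diagnosis of PC (International Classification of Diseases, 10th Revision, Clinical Modification [ICD-10-CM] C61". Section 9.2.2 then excludes patients who "Had any other primary cancer (excluding non-melanoma skin cancer) during the baseline period", and the abstract repeats the same rule. Neither place prints codes or points to an appendix.

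At the end of Appendix Table 2 (Annex 2) is a row labelled 'Primary cancers' with the codes "C00-C21, C22.1-C22.7, C23-C76, C80.1, C80.2, C81-C96, C7A". It carries no footnote, no exception and no reference to eligibility.

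Section 9.5 says that the number of eligible patients "will be determined in accordance with the sample selection conducted per the criteria described in Section 9.2". Annex 1 lists no stand-alone documents.

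**The concern.** The criterion needs a list of malignancies that are primary, are not prostate cancer and are not non-melanoma skin cancer. The one list in the visible text that could serve is not that list. It contains two categories that the criterion leaves out and lacks two codes that the criterion appears to cover.

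This list would help define the cohort, and every objective, including the primary one, is analysed in that cohort. A programmer working from Section 9.2.2 and another working from Annex 2 could therefore build different study populations from the same protocol. The excess codes would remove patients who should stay. The missing codes would keep patients who should go.

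**Working it through.** The plan states no figure on this point, so there is none to reproduce. The check sets the row against the criterion, code by code.

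**Inputs**
- Inclusion code: C61 (Section 9.2.1).
- Exclusion rule: other primary cancer, non-melanoma skin cancer exempt, 365-day baseline (Section 9.2.2).
- Code row: seven entries (Appendix Table 2).
- Assumption from the public ICD-10-CM code system, which the protocol uses but does not spell out: C44 is the non-melanoma skin cancer category, and C22.0 and C22.8 are primary liver cancer codes. The C61 result does not depend on this.

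**Step 1: does the row have another use?** Table 2 in Section 9.3 says of comorbidities: "A binary variable (yes/no) will be created for patients with a diagnosis of each of the following comorbidities during the baseline period". It lists 18 conditions, and none is a cancer in its own right. The NCI index block of Appendix Table 2 has 11 rows, and none is a cancer. Site of metastasis needs secondary-tumour codes, and the row omits C77-C79. The exclusion is the only visible rule that calls for a list of primary cancers.

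**Step 2: membership of each code in the seven entries**

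| Code | Entry that contains it | Criterion requires | Match? |
|---|---|---|---|
| C61 | C23-C76 | not on the list (study disease) | no |
| C44 | C23-C76 | not on the list (exempt) | no |
| C22.0 | none | on the list | no |
| C22.8 | none | on the list | no |
| C22.9, C77-C79, C80.0 | none | not needed in a list limited to primary tumours | yes |

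**Step 3: effect of literal use.** With C61 on the list, every patient with a prostate cancer code in the baseline year would be excluded. Only patients whose C61 codes all fall outside that year would remain. With C44 on the list, patients whose only other cancer code is C44 would be excluded although they are exempt. With C22.0 and C22.8 absent, patients whose only other cancer code is one of these would be kept.

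**Step 4: the replacement range.** C23-C76 holds 76 − 23 + 1 = 54 numeric three-character categories. C23-C43 holds 21, C45-C60 holds 16 and C62-C76 holds 15, and 21 + 16 + 15 = 52. The difference, 54 − 52 = 2, is exactly C44 and C61.

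**Step 5: C4A.** The row names C7A separately but not C4A. If ranges are read as integers, C4A matches nothing. If they are compared as character strings with letters sorting after digits, C4A falls inside C23-C76 and also inside the replacement C45-C60. Changing the range does not settle how C4A is treated, so it has to be named.

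**The case against.** The best defence is that the row is labelled 'Primary cancers', not 'Other primary cancers', and is true to that label. On this view the row is a generic list, and the criterion does the subtraction: its wording sets aside the study disease and non-melanoma skin cancer. No text says that the row alone defines the exclusion, so the link between the two is inferred. Figure 1 follows the criteria, is not visible, and might carry codes.

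Much of this stands. The intent of Section 9.2.2 is clear, and a careful programmer would drop both C61 and C44. Those two entries are errors only if the row is applied as printed. The absent cross-reference is not peculiar to this criterion, since no appendix table is cited anywhere in the visible body, and it shows no harm by itself.

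The defence does not reach the liver codes. A criterion that only subtracts cannot add C22.0 and C22.8 to a list that lacks them. Nor does the row read as loose shorthand: it selects at subcode level within C22 and C80, and no reason is given for leaving these two out.

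A reader might infer three stronger points, which the documents do not support:
- *The cohort will be built wrongly.* The documents show a faulty list, not a faulty program. Literal use of C61 would remove nearly the whole cohort and would very likely be noticed.
- *Quality control would miss the error.* Section 9.8 says: "The audit process both confirms the validity of the analytical approach and ensures that all programs and results are accurate". That is not confined to checking programs against the printed list, and an audit against the written criterion could catch the skin cancer entry.
- *The race comparisons in Objectives 5 to 7 would be biased.* That would need the affected codes to differ in frequency between Black and non-Hispanic White patients, and the documents give no rates.

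**Conclusion.** The point holds as a minor error in the text as written. The code row that would implement a cohort-defining exclusion has two categories too many (C61, C44) and two subcodes too few (C22.0, C22.8). The first pair does harm only under literal use. The second pair is not repaired by reading the criterion with care.

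Its size can be stated in codes but not in patients, because the documents give no prevalence for any of these codes. An assumed baseline C44 frequency of 1% to 10% would mean 10 to 100 exempt patients lost per 1,000 under literal use. That only scales an assumption and is not evidence about this study.

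The conclusion assumes that the row is meant for Section 9.2.2, that Figure 1 holds no competing list, and that the ICD-10-CM meanings given in the working are accepted. Confidence is high about what the row contains and does not extend to how many patients are affected.

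**What to change.** In Appendix Table 2, before cohort programming:

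1. Relabel the row 'Other primary cancers (exclusion, Section 9.2.2)'. This turns the inferred link into a stated one.
2. Replace C23-C76 with C23-C43, C45-C60, C62-C76.
3. Add C22.0 and C22.8, or state why they are left out.
4. State explicitly whether C4A counts as exempt non-melanoma skin cancer.

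The cost is an edit to one row of Annex 2. It needs no new data and no added analysis.

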Appendix Table 3. Codes for corticosteroids and pain medications

Treatment	GPI	HCPCS
Corticosteroids	22, 8910, 8915	C9256, J0702, J0704, J1020, J1030, J1040, J1094, J1100, J1700, J1710, J1720, J2650, J2920, J2930, J3300, J3301, J3302, J3303, J7312, J7506, J7509, J7510, J7512, J7624, J7626, J7627, J7633, J7634, J7637, J7638, J7683, J7684, J8540
Pain medications (analgesics)		
Opioids	65	

Abbreviations: GPI: Generic Product Identifier; HCPCS: Healthcare Common Procedure Coding System
